6.1.5.5 Second Course Phase (Retreatment Period)

Subjects who stop pembrolizumab with SD or better may be eligible for up to one year of additional pembrolizumab therapy if they progress after stopping study treatment. This retreatment is termed the Second Course Phase of this study and is only available if the study remains open and the subject meets the following conditions:

- Had SD, PR or CR and stopped pembrolizumab treatment after 24 months of study therapy for reasons other than disease progression or intolerance

AND

- Experienced an investigator-determined confirmed radiographic disease progression after stopping their initial treatment with pembrolizumab
- Did not receive any anti-cancer treatment since the last dose of pembrolizumab
- Has a performance status of 0 to 2 on the ECOG Performance Scale
- Demonstrates adequate organ function as detailed in Section 5.1.2
- Female subject of childbearing potential should have a negative serum or urine pregnancy test within 72 hours prior to receiving retreatment with study medication.
- Female subject of childbearing potential should be willing to use 2 methods of birth control or be surgically sterile, or abstain from heterosexual activity for the course of the study through 120 days after the last dose of study medication (Reference Section 5.7.2). Subjects of child bearing potential are those who have not been surgically sterilized or have been free from menses for > 1 year.
- Male subject should agree to use an adequate method of contraception starting with the first dose of study therapy through 120 days after the last dose of study therapy.
- Does not have a history or current evidence of any condition, therapy, or laboratory abnormality that might interfere with the subject's participation for the full duration of the trial or is not in the best interest of the subject to participate, in the opinion of the treating investigator.

Subjects who restart treatment will be retreated at the same dose and dose interval as when they last received pembrolizumab. Treatment will be administered for up to one additional year.

Visit requirements are outlined in Section 6.0 – Trial Flow Chart.

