4.1.2 Subject Inclusion Criteria

In order to be eligible for participation in this trial, the subject must:

1. Be willing and able to provide written informed consent/assent for the trial.
2. Be ≥ 18 years of age on day of signing informed consent.
3. Have measurable disease based on RECIST 1.1.
4. Be willing to provide tissue from a newly obtained core or excisional biopsy of a tumor lesion. *Newly-obtained is defined as a specimen obtained up to 6 weeks (42 days) prior to initiation of treatment on Day 1. Subjects for whom newly-obtained samples cannot be provided (e.g. inaccessible or subject safety concern) may submit an archived specimen only upon agreement from the Principle Investigator.*
5. Have a performance status of **0 to 2** on the ECOG Performance Scale.
6. Demonstrate adequate organ function as defined in Table 1, all screening labs should be performed within 10 days of treatment initiation.

Table 1 Adequate Organ Function Laboratory Values

System	Laboratory Value
Hematological	
Absolute neutrophil count (ANC)	$\geq 1,500 / \mu\text{L}$

Platelets	$\geq 100,000 / \text{mcL}$
Hemoglobin	$\geq 9 \text{ g/dL}$ or $\geq 5.6 \text{ mmol/L}$ without transfusion or EPO dependency (within 7 days of assessment)
Renal	
Serum creatinine OR Measured or calculated ^a creatinine clearance (GFR can also be used in place of creatinine or CrCl)	$\leq 1.5 \times$ upper limit of normal (ULN) OR $\geq 60 \text{ mL/min}$ for subject with creatinine levels $> 1.5 \times$ institutional ULN
Hepatic	
Serum total bilirubin	$\leq 1.5 \times$ ULN OR Direct bilirubin \leq ULN for subjects with total bilirubin levels $> 1.5 \text{ ULN}$
AST (SGOT) and ALT (SGPT)	$\leq 2.5 \times$ ULN OR $\leq 5 \times$ ULN for subjects with liver metastases
Albumin	$> 2.5 \text{ g/L}$
Coagulation	
International Normalized Ratio (INR) or Prothrombin Time (PT)	$\leq 1.5 \times$ ULN unless subject is receiving anticoagulant therapy as long as PT or PTT is within therapeutic range of intended use of anticoagulants
Activated Partial Thromboplastin Time (aPTT)	$\leq 1.5 \times$ ULN unless subject is receiving anticoagulant therapy as long as PT or PTT is within therapeutic range of intended use of anticoagulants

^aCreatinine clearance should be calculated per institutional standard.

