10. Has active autoimmune disease that has required systemic treatment in the past 2 years (i.e. with use of disease modifying agents, corticosteroids or immunosuppressive drugs). Replacement therapy (eg., thyroxine, insulin, or

physiologic corticosteroid replacement therapy for adrenal or pituitary insufficiency, etc.) is not considered a form of systemic treatment.

11. Has known history of, or any evidence of active, non-infectious pneumonitis.
12. Has an active infection requiring systemic therapy.
13. Has a history or current evidence of any condition, therapy, or laboratory abnormality that might confound the results of the trial, interfere with the subject's participation for the full duration of the trial, or is not in the best interest of the subject to participate, in the opinion of the treating investigator.
14. Has known psychiatric or substance abuse disorders that would interfere with cooperation with the requirements of the trial.
15. Is pregnant or breastfeeding, or expecting to conceive or father children within the projected duration of the trial, starting with the pre-screening or screening visit through 120 days after the last dose of trial treatment.
16. Has received prior therapy with an anti-PD-1, anti-PD-L1, or anti-PD-L2 agent.
17. Has a known history of Human Immunodeficiency Virus (HIV) (HIV 1/2 antibodies).
18. Has known active Hepatitis B (e.g., HBsAg reactive) or Hepatitis C (e.g., HCV RNA [qualitative] is detected).
19. Has received a live vaccine within 30 days of planned start of study therapy.

Note: Seasonal influenza vaccines for injection are generally inactivated flu vaccines and are allowed; however intranasal influenza vaccines (e.g., Flu-Mist®) are live attenuated vaccines, and are not allowed.

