6.1.3 Laboratory Procedures/Assessments

Details regarding specific laboratory procedures/assessments to be performed in this trial are provided below Laboratory Safety Evaluations (Hematology, Chemistry and Urinalysis)

Laboratory tests for hematology, chemistry, urinalysis, and others are specified in Table 5.

Table 5 Laboratory Tests

Hematology	Chemistry	Urinalysis	Other
FBC	Albumin	Blood	Serum β -human chorionic gonadotropin †
Hemoglobin	Alkaline phosphatase	Glucose	(β -hCG)†
Platelet count	Alanine aminotransferase (ALT)	Protein	PT (INR)
WBC (total and differential)	Aspartate aminotransferase (AST)	Specific gravity	aPTT
Absolute Neutrophil Count	Lactate dehydrogenase (LDH)	Microscopic exam (If abnormal)	Free thyroxine (T4)
Absolute Lymphocyte Count	Uric Acid	results are noted	Thyroid stimulating hormone (TSH)
	Calcium	Urine pregnancy test †	ACTH
	Chloride		Cortisol (morning sample)
	Glucose		
	Phosphorus		
	Potassium		
	Sodium		
	Magnesium		
	Total Bilirubin		
	Direct Bilirubin (If total bilirubin is elevated above the upper limit of normal)		

† Perform on women of childbearing potential only. If urine pregnancy results cannot be confirmed as negative, a serum pregnancy test will be required.

SWIPE Protocol Version: 1.1 June, 2017

Laboratory tests for screening or entry into the Second Course Phase should be performed within 10 days prior to the first dose of treatment. After Cycle 1, pre-dose laboratory procedures can be conducted up to 72 hours prior to dosing. Results must be reviewed by the investigator or qualified designee and found to be acceptable prior to each dose of trial treatment.

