7.2 Statistical Analysis Plan

Comparator data regarding patients' outcomes receiving maintenance therapy can be obtained from the Pemetrexed continuation and Erlotinib switch maintenance studies.

The best available data for maintenance treatment of non-squamous NSCLC patients come from the continuation Pemetrexed trial (Pas Ares¹⁶). This trial enrolled good performance status patients (PS 0-1), with non-squamous histology, who did not progress after 4 cycles of Pemetrexed / Cisplatin, and continued Pemetrexed chemotherapy, resulting in a 1-year PFS of 18.6%, whilst in the placebo arm the 1 year PFS was 5%.

For the squamous patients, the best available data come from the switch maintenance Erlotinib trial²¹ (SATURN), given that Erlotinib is the only agent approved for maintenance treatment in patients with squamous cancers. The 1-year PFS for the erlotinib arm is slightly above placebo, around 6%.

Hence for the comparator arm by using:

- data from the Pemetrexed continuation study for non squamous histology: 1-year PFS of 18% for non squamous on Pemetrexed maintenance,
- data from the erlotinib arm in the SATURN trial for patients with squamous histology and estimating 1-year PFS of 6% for squamous patients
- whilst assuming a ratio of 1:1 adenocarcinomas to squamous,
- provides us a weighted average of 12% of 1-year PFS

Assume irPFS at 1 year for the maintenance Pembrolizumab arm to be 25%, compared to 12% in the normal chemotherapy maintenance arm.

Sample size for Fleming one stage Phase II trials

Probability of Type I Error (α) = 0.05

Power ($1 - \beta$) = 0.8

Lower proportion for rejection (p_0) = 0.12

Higher proportion for acceptance (p_n) = 0.25

Sample size required = 48

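### The albumin limit in Table 1 is written as > 2.5 g/L, which in practice excludes nobody at entry or retreatment; the evident intended unit is g/dL

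*Combined protocol and SAP*

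**What the plan says.** Entry is governed by inclusion criterion 6 in section 4.1.2: "Demonstrate adequate organ function as defined in Table 1, all screening labs should be performed within 10 days of treatment initiation". Table 1, which follows it, gives the albumin limit as > 2.5 g/L. In the same table the haemoglobin limit is given in g/dL.

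Retreatment takes up the same limits by two routes. Section 6.1.5.5 lists among its conditions: "Demonstrates adequate organ function as detailed in Section 5.1.2". Section 4.8.1, on stopping after a complete response, requires a patient who later progresses to meet the safety parameters in the inclusion and exclusion criteria. Section 6.1.3 has the tests repeated for this purpose: "Laboratory tests for screening or entry into the Second Course Phase should be performed within 10 days prior to the first dose of treatment". Table 5 in that section includes albumin in the chemistry panel.

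No other section states an albumin limit or corrects the unit in Table 1.

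**The concern.** A numeric eligibility limit is there to decide who may be treated. In Table 1 the albumin number and its unit do not belong together: 2.5 is a plausible lower limit in g/dL but not in g/L. Read literally, the line is passed by every patient, so albumin is measured at screening and before a second course but the stated limit never acts on the result.

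What is at stake is one stated safety screen, and the record of who met the criteria. A patient with albumin of, say, 20 g/L is eligible under the text as written. The same patient would be a protocol deviation to a monitor who silently reads the limit as g/dL.

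**Working it through.** **What there is to reproduce.** The albumin limit is not derived from a formula, so it has no calculation behind it. The one derived figure used below is the sample size (section 7.2: "Sample size required = 48"). The one-sided normal approximation for a single-stage design, with p0 = 0.12, p1 = 0.25, alpha = 0.05 and power = 0.80, is

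n = [(1.645 × √(0.12 × 0.88) + 0.842 × √(0.25 × 0.75)) / (0.25 − 0.12)]² = 47.8, rounded up to 48.

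This matches the plan. Albumin is not an input, so the unit error leaves sample size, alpha and power untouched.

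**Unit conversion.** 1 g/dL = 10 g/L. The written limit is therefore 2.5 / 10 = 0.25 g/dL. The same number in g/dL would be 2.5 × 10 = 25 g/L, ten times the written value.

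**Against physiological values.** Assumption, not in the documents: adult albumin is normally about 35-50 g/L, and severely low values are about 15-25 g/L.

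- Normal range over the written limit: 35 / 2.5 = 14 and 50 / 2.5 = 20.
- Severely low range over the written limit: 15 / 2.5 = 6 and 25 / 2.5 = 10.

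A limit of 25 g/L falls at the upper edge of the assumed severely low range, where such a limit would be expected to bite. A limit of 2.5 g/L falls far below that range.

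**How many would fail.** The documents give no albumin distribution, so normal distributions are assumed over a range of means and SDs. A patient fails when albumin is at or below the limit L, so P(fail) = Φ((L − mean) / SD), and the expected number is 48 × P(fail).

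| Assumed mean, SD (g/L) | P(fail), L = 2.5 g/L | Expected of 48 | P(fail), L = 25 g/L | Expected of 48 |
|---|---|---|---|---|
| 40, 4 | about 0 | about 0 | 0.009% | 0.004 |
| 35, 6 | 0.000003% | 0.0000015 | 4.8% | 2.3 |
| 30, 7 | 0.004% | 0.002 | 23.8% | 11.4 |
| 25, 7 | 0.065% | 0.03 | 50% | 24 |

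The last row is a deliberate extreme, included to stress the written limit; it is not a plausible trial population. Even there the written limit is expected to exclude 0.03 of 48 patients.

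**Which section the retreatment rule means.** Section 5.0 is the flow chart and contains no 5.1.2. The protocol's internal references often run one number too high: 5.7.2 is cited for contraception, which is 4.7.2; 5.2.1 for dose modification, which is 4.2.1; and 7.1.5.5 for the second course, which is 6.1.5.5. By the same shift 5.1.2 is 4.1.2, the section that holds Table 1. The albumin line therefore applies at retreatment as well as at entry.

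**The case against.** Several objections carry weight.

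- **The unit may be a conversion fault.** One letter separates g/L from g/dL, and converting a table to text could drop it. This cannot be ruled out entirely, but haemoglobin in the same table kept its g/dL and nothing else suggests that the albumin line is damaged. The sponsor can settle it from the source file.
- **Other safeguards remain.** Exclusion criterion 13 (section 4.1.3) lets the investigator exclude for a "laboratory abnormality that might confound the results of the trial" or where taking part is not in the patient's interest. The last condition in section 6.1.5.5 repeats much of this for the second course. Section 6.1.3 requires laboratory results to be reviewed and judged acceptable before every dose. All of this stands: a severely hypoalbuminaemic patient who passes the albumin line is not thereby admitted. These are matters of judgement, though, and do not replace a stated limit.
- **A clinician would notice.** The unit is implausible enough that many would query it or read it as g/dL. That is likely, but then the operating rule is not the written one.
- **Retreatment will be rare.** Under section 6.1.5.5 it follows 24 months of therapy, while the trial summary expects an average of 6 cycles. The retreatment consequence is therefore small; the entry consequence is the main one.

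A reader might go further and infer that the whole organ-function criterion screens out nobody. It does not follow: neutrophils, platelets, haemoglobin, creatinine, bilirubin, transaminases and coagulation all have limits in Table 1 that work. A reader might also infer that different sites would admit different patients. The documents do not support that, because patients are identified by the treating oncologists and screened by one Clinical Trials Unit (section 6.1.5.1), and records are kept at that centre (section 9.6). What remains is a possible difference between investigator and monitor. Nor is the absence of a unit for albumin in Table 5 a separate fault, since that table gives no unit for any analyte.

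**Conclusion.** The point holds for the albumin line of Table 1. As written it excludes nobody in practice, at first entry or at retreatment. This rests on one outside assumption, that adult albumin does not fall to anywhere near 2.5 g/L even when severely low (taken as about 15-25 g/L). The conclusion was the same under all four assumed distributions.

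That g/dL was intended is an inference from the number itself; the documents do not state it. The effect of a working limit cannot be sized from the documents. The figures of about 0, 2.3 and 11.4 of 48 are illustrations under assumed means of 40, 35 and 30 g/L. The error concerns eligibility and safety screening only and gives no ground for questioning the design calculation. It is a small correction, but it belongs to a rule the trial applies to every entrant, so it should be made.

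**What to change.** Change the albumin entry in Table 1 to > 2.5 g/dL (25 g/L), once the sponsor has confirmed that this is the intended limit. In section 6.1.5.5, replace the reference to 5.1.2 with section 4.1.2, Table 1.

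The cost is one table entry and one cross-reference in an amendment. No new test is needed, because albumin is already in the chemistry panel. The downside is that some patients who pass the literal text may be excluded once the limit works; the number is probably small but depends on the albumin levels of patients coming off platinum chemotherapy, which the documents do not describe. Patients already enrolled met the text in force, so the correction should apply from the amendment onward and need not turn earlier entries into deviations.

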6.2 Assessing and Recording Adverse Events

An adverse event is defined as any untoward medical occurrence in a patient or clinical investigation subject administered a pharmaceutical product and which does not necessarily have to have a causal relationship with this treatment. An adverse event can therefore be any unfavorable and unintended sign (including an abnormal laboratory finding, for example), symptom, or disease temporally associated with the use of a medicinal product or protocol-specified procedure, whether or not considered related to the medicinal product or protocol-specified procedure. Any worsening (i.e., any clinically significant adverse change in frequency and/or intensity) of a preexisting condition that is temporally associated with the use of the Merck's product, is also an adverse event.

Changes resulting from normal growth and development that do not vary significantly in frequency or severity from expected levels are not to be considered adverse events. Examples of this may include, but are not limited to, teething, typical crying in infants and children and onset of menses or menopause occurring at a physiologically appropriate time.

Merck product includes any pharmaceutical product, biological product, device, diagnostic agent or protocol-specified procedure, whether investigational (including placebo or active comparator medication) or marketed, manufactured by, licensed by, provided by or distributed by Merck for human use.

Adverse events may occur during the course of the use of Merck product in clinical trials, or as prescribed in clinical practice, from overdose (whether accidental or intentional), from abuse and from withdrawal.

Progression of the cancer under study is not considered an adverse event.

All adverse events that occur after the consent form is signed but before treatment allocation/randomization must be reported by the investigator if they cause the subject to be excluded from the trial, or are the result of a protocol-specified intervention, including but not limited to washout or discontinuation of usual therapy, diet, placebo treatment or a procedure.

From the time of treatment allocation/randomization through 30 days following cessation of treatment, all adverse events must be reported by the investigator. Such events will be recorded at each examination on the Adverse Event case report forms/worksheets. The reporting timeframe for adverse events meeting any serious criteria is described in section 7.2.3.1. The investigator will make every attempt to follow all subjects with non-serious adverse events for outcome.

6.2.1 Definition of an Overdose for This Protocol and Reporting of Overdose to the Sponsor and to Merck

For purposes of this trial, an overdose of pembrolizumab will be defined as any dose of 1,000 mg or greater (≥ 5 times the indicated dose). No specific information is available on the treatment of overdose of pembrolizumab. Appropriate supportive treatment should be provided if clinically indicated. In the event of overdose, the subject should be observed closely for signs of toxicity. Appropriate supportive treatment should be provided if clinically indicated.

If an adverse event(s) is associated with (“results from”) the overdose of a Merck product, the adverse event(s) is reported as a serious adverse event, even if no other seriousness criteria are met.

If a dose of Merck’s product meeting the protocol definition of overdose is taken without any associated clinical symptoms or abnormal laboratory results, the overdose is reported as a non-serious Event of Clinical Interest (ECI), using the terminology “accidental or intentional overdose without adverse effect.”

All reports of overdose with and without an adverse event must be reported within 24 hours to the Sponsor and within 2 working days hours to Merck Global Safety. (Attn: Worldwide Product Safety; [contact])

6.2.2 Reporting of Pregnancy and Lactation to the Sponsor and to Merck

Although pregnancy and lactation are not considered adverse events, it is the responsibility of investigators or their designees to report any pregnancy or lactation in a subject (spontaneously reported to them) that occurs during the trial.

Pregnancies and lactations that occur after the consent form is signed but before treatment allocation/randomization must be reported by the investigator if they cause the subject to be excluded from the trial, or are the result of a protocol-specified intervention, including but not limited to washout or discontinuation of usual therapy, diet, placebo treatment or a procedure.

Pregnancies and lactations that occur from the time of treatment allocation/randomization through 120 days following cessation of Sponsor’s product, or 30 days following cessation of treatment if the subject initiates new anticancer therapy, whichever is earlier, must be reported by the investigator. All reported pregnancies must be followed to the completion/termination of the pregnancy. Pregnancy outcomes of spontaneous abortion, missed abortion, benign hydatidiform mole, blighted ovum, fetal death, intrauterine death, miscarriage and stillbirth must be reported as serious events (Important Medical Events). If the pregnancy continues to term, the outcome (health of infant) must also be reported.

Such events must be reported within 24 hours to the Sponsor and within 2 working days to Merck Global Safety. (Attn: Worldwide Product Safety; [contact])

6.2.3 Immediate Reporting of Adverse Events to the Sponsor and to Merck

6.2.3.1 Serious Adverse Events

A serious adverse event is any adverse event occurring at any dose or during any use of Merck's product that:

- Results in death;
- Is life threatening;
- Results in persistent or significant disability/incapacity;
- Results in or prolongs an existing inpatient hospitalization;
- Is a congenital anomaly/birth defect;
- Is another important medical event

• **Note:** In addition to the above criteria, adverse events meeting either of the below criteria, although not serious per ICH definition, are reportable to the Merck in the same timeframe as SAEs to meet certain local requirements. Therefore, these events are considered serious by Merck for collection purposes.

- Is a new cancer (that is not a condition of the study);
- Is associated with an overdose.

Refer to Table 6 for additional details regarding each of the above criteria.

For the time period beginning when the consent form is signed until treatment allocation/randomization, any serious adverse event, or follow up to a serious adverse event, including death due to any cause other than progression of the cancer under study (reference Section 7.2.3.3 for additional details) that occurs to any subject must be reported within 24 hours to the Sponsor and within 2 working days to Merck Global Safety if it causes the subject to be excluded from the trial, or is the result of a protocol-specified intervention, including but not limited to washout or discontinuation of usual therapy, diet, placebo treatment or a procedure.

For the time period beginning at treatment allocation/randomization through 90 days following cessation of treatment, or 30 days following cessation of treatment if the subject initiates new anticancer therapy, whichever is earlier, any serious adverse event, or follow up to a serious adverse event, including death due to any cause other than progression of the cancer under study (reference Section 7.2.3.3 for additional details), whether or not related to the Merck product, must be reported within 24 hours to the Sponsor and within 2 working days to Merck Global Safety.

Additionally, any serious adverse event, considered by an investigator who is a qualified physician to be related to Merck product that is brought to the attention of the investigator at any time following consent through the end of the specified safety follow-up period specified in the paragraph above, or at any time outside of the time period specified in the previous paragraph also must be reported immediately to the Sponsor and to Merck Global Safety.

SWIPE Protocol Version: 1.1 June, 2017

All subjects with serious adverse events must be followed up for outcome.

SAE reports and any other relevant safety information are to be forwarded to the Merck Global Safety [contact]

A copy of all 15 Day Reports and Annual Progress Reports is submitted as required by FDA, European Union (EU), Pharmaceutical and Medical Devices agency (PMDA) or other local regulators. Investigators will cross reference this submission according to local regulations to the Merck Investigational Compound Number (IND, CSA, etc.) at the time of submission. Additionally investigators will submit a copy of these reports to Merck & Co., Inc. (Attn: Worldwide Product Safety; [contact]) at the time of submission to FDA.

